### 4.2.4 SAFETY ANALYSIS SET

The safety analysis set (SAF) consists of all subjects who receive at least one dose of study drug. Treatment groups will be determined using the actual treatment received, regardless of the randomization treatment assignment. The SAF is the primary analysis set for safety analyses.

### 4.2.5 PK & BIOMARKER ANALYSIS SET

The PK & biomarker analysis set will include all randomized subjects who receive at least 1 dose of study drug and who have at least one valid analytical result at baseline, at least one post-dose analytical result and had no major relevant protocol or dosing deviations that could potentially affect the PK and/or PD profile. The PK & biomarker analysis set will be used for the summaries of all PK, PD, and biomarker data. All PK, PD, and biomarker parameters are summarized in [Section 7](#).

#### 4.3 HANDLING OF DATA

In general, missing data will not be imputed unless methods for handling missing data are specified. For purposes of the DRC safety assessment, all results will be presented ‘as observed’ with missing values not imputed. The handling of missing data in analyses of the efficacy endpoints is discussed in Section 6.2.4.

If multiple valid, non-missing, continuous measurements or visits (regardless if it’s scheduled or unscheduled) occurring within a single visit, records will be chosen based on the following rules if a single value is needed:

- For baseline, the baseline value will be the last non-missing value prior to the first dosing of study drug; if multiple measurements occur on the same day, the last non-missing value prior to the time of first dosing of study drug will be considered as the baseline value. If these multiple measurements occur at the same time or the time is not available, the average of these measurements will be considered the baseline value.
- For post-baseline values:
  - a. The record closest to the nominal day for that visit will be selected.
  - b. If there are 2 records that are equidistant from the nominal day, the later record will be selected.
  - c. If there is more than 1 record on the selected day, the average will be taken.

If multiple valid, non-missing, categorical observations exist for one visit, records will be selected as follow:

- For baseline, the last available record prior to the first dose of study drug will be selected. If there are multiple records at the same time or no time recorded on the same day, the worst value will be selected unless otherwise specified.
- For post-baseline values:
  - a. The record closest to the nominal day for that visit will be selected.
  - b. If there are 2 records that are equidistant from the nominal day, the later record will be selected.
  - c. If there is more than 1 record on the selected day, the value with the worst severity will be used.

#### 5 STUDY SUBJECTS

Unless otherwise specified, all available subject data will be listed and summary tables for disposition and protocol deviations will be presented for the SAF as described in [Table 2](#).

**Table 2. Data Presentation for Study Subject Information**

Data	Variables	Presentation
Subject Disposition	Subject, screen failures, reason for screen fail, subject study status by phase (e.g., in study, completed, discontinued, etc.), reason for discontinuation,	

• n of subjects screened

• n of subjects randomized

• n and % of subjects included in each analysis set.

• n of subjects treated

• n and % of subjects who completed IBT phase

• n and % of subjects discontinued by primary reason for discontinuation

• n and % of subjects that had a protocol deviation in CBT/OL phase

• n and % of subjects in clinical response at CCI [REDACTED]

• n and % of subjects in clinical remission at CCI [REDACTED]

• n and % of subjects who enter CBT phase

• n and % of subjects who enter CBT phase and successfully taper off corticosteroids

• n and % of subjects who completed CBT phase

• n and % of subjects who enter OL phase

• n and % of subjects who completed OL phase

Summary of Protocol Deviations	Subject, major/minor protocol deviations	

• n and % of subjects that had a protocol deviation by treatment group. Both major and minor protocol deviations will be listed.

Summary of Demographics and Baseline Disease Characteristics	age, sex, race, ethnicity, height, weight, body mass index, duration of UC, prior advanced therapy use (yes/no), systemic corticosteroid use at baseline (yes/no) baseline disease characteristics (mMCS, MES, RB, SF, PGA)	

• n and % of subjects for each demographic variable

Summary of Medical History	All medical events sorted by system organ class (SOC) and preferred term (PT)	

• n and % of subjects for each medical event

Summary of Prior Medications	All medications taken prior to study drug administration.	

• n and % of subjects for each concomitant medication listed by ATC Classification level 2 and preferred term

Summary of Concomitant Medications	All medications taken on or after the date of first study drug administration.	

• n and % of subjects for each concomitant medication listed by ATC Classification level 2 and preferred term

Summary of Treatment Compliance	Duration of exposure, number of doses received, subjects with $\geq 1$ missed dose, and	

• n, mean, SD, median, min, and max number of days on treatment

• n, mean, SD, median, min, and max number of doses given

	number of missed doses will be summarized.	
 
• n and % of subjects who missed <math>\geq 1</math> dose
 
• n, mean, SD, median, min, and max missed doses
 
• 
 

--	--	---

ATC = anatomical therapeutic chemical; CBT = continued blinded treatment; IBT = initial blinded treatment; max = maximum; min = minimum; N = number of subjects in a group; OL = open-label; UC = ulcerative colitis; MCS = total mayo clinic score; MES = mayo endoscopic subscore; RB = rectal bleeding; SF = stool frequency; PGA = physician's global assessment

## 5.1 SUBJECT DISPOSITION

Subject disposition will be summarized for all subjects screened in this study. Total screened subjects and screen failed subjects will be expressed as overall counts. A summary and by-subject listing of subject disposition will be provided by treatment group for each phase in the study. This summary will present number and percentage of subjects randomized, discontinued, and completed for each study period. The number of subjects in each of the analysis sets will also be included. The reasons for premature discontinuation from treatment period as recorded in the eCRFs will be summarized. Number of subjects who reach clinical response and clinical remission at **CCI** will also be summarized.

The following by-subject listings will be provided by subject identification number in ascending order to support the above summary table:

- Reasons for premature study discontinuation
- Reasons for screen failure
- Reasons for re-screening

## 5.2 PROTOCOL DEVIATIONS

Protocol deviations will be summarized by type in each treatment group for each study phase. The number and percentage of subjects with protocol deviations will be summarized as major or minor by treatment group.

A by-subject listing will be provided for those subjects with any protocol deviations. A complete list of possible protocol deviations and how they are classified, tracked, and managed can be found in the PT101-201 protocol deviation plan.

## 5.3 DEMOGRAPHICS AND BASELINE CHARACTERISTICS

Subject demographic and baseline disease characteristics will be summarized for each treatment group and pooled across treatment groups. Demographic characteristics include age (years), sex (male/female), race/ethnicity, baseline body weight (kg), baseline height (cm), and baseline body mass index (BMI: kg/m^2). Baseline disease characteristics include duration of UC (years), tumor necrosis factor-alpha (TNF- $\alpha$ ) exposure, prior advanced therapy use (yes/no), systemic corticosteroid use at baseline (yes/no), baseline disease measures (mMCS, RB, SF, MES, PGA). The summary of demographic data will be provided for the SAF and ITT.

Certain characteristics, that are collected at baseline or after baseline but not summarized in the demographic summary, will be reported as a listing.

## 5.4 MEDICAL, SURGICAL, AND MEDICATION HISTORY

Medical and surgical history will be coded using the most current available version of the MedDRA (version 25.1 or newer) and will include all relevant surgical and medical history including UC-related complications, other significant conditions or diseases relevant to the disease under study.

A summary table and by-subject listing will be provided for those subjects with any medical/surgical history for the SAF. No formal statistical testing is planned.

## 5.5 PRIOR AND CONCOMITANT MEDICATION

For the purposes of subgroup identification, prior and concomitant medications will be classified into anatomical therapeutic chemical (ATC) drug classes using the WHODD version September 2022 or newer.

Summaries of prior and concomitant medications will include the number and percentage of subjects by ATC classification level 2 and preferred term (PT). A subject will be counted only once within a given drug class and within a given drug name, even if he/she received the same medication at different times. If any prior or concomitant medication is classified into multiple ATC classes, the medication will be summarized separately under each of these ATC classes. The summary tables will be sorted by alphabetical order by drug class and drug name. In case any specific medication does not have ATC classification level 2 coded term, it will be summarized under “Unavailable ATC classification” category. Summaries will be based on the SAF.

All prior and concomitant medications will be provided in a by-subject listing with the relevant information collected by treatment group.

### 5.5.1 PRIOR MEDICATION

Prior medication is defined as any medication stopped before the date of study drug administration. If the stop date is unknown or incomplete and the medications cannot definitely be considered as stopped prior to first dosing date then the medications will be considered as concomitant medications (e.g., partial stop date is May 2021, first dosing date is 15 May 2021, medication will be considered as concomitant).

### 5.5.2 CONCOMITANT MEDICATION

Any medication with a start date prior to or on the first dosing date and continuing to take after the first dosing date or started after the first dosing date will be considered concomitant medications. If the start date of a medication is incomplete or missing, the medication will be assumed to be concomitant medication, unless the incomplete start date (month and/or year) or the stop date (complete or incomplete) clearly indicate that the medication stopped prior to first dosing date. Medication with completely missing start and stop dates will be included in the concomitant medication summary. Concomitant medications will be summarized for each study phase and listed. Additionally, a summary and listing of subjects who tapered off corticosteroids will be provided.

## 5.6 TREATMENT COMPLIANCE

Treatment exposure will be summarized and listed using descriptive statistics. Duration of exposure, number of doses, and cumulative total dose given (mg) will be summarized. Dose modifications, if any, will be included as a listing. Total duration of exposure to study treatment is defined as follows:

Duration of exposure during the IBT phase will be calculated as:

*“Date of last study visit in IBT – Date of first dosing date + 1”*

Duration of exposure during the CBT phase will be calculated as:

*“Date of last study visit in CBT phase – Date of the CBT Visit 1 dosing of study treatment + 1”*

Duration of exposure during the OL phase will be calculated as:

*“Date of last study visit in OL – Date of the OL Visit 1 dosing of study treatment + 1”*

Frequency distributions and descriptive statistics for extent of exposure will be provided by treatment group for the SAF.

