3.1.4 Early Termination or Unscheduled Visit

Subjects who receive \geq 1 dose of study drug should be encouraged to complete all study visits within the IBT phase. If subjects discontinue study drug and terminate early from the study, they will be asked to return to the study site for an early termination (ET) visit approximately 28 days after the last dose of study drug administration. If a subject has an ET visit, the assessments designated in the schedule of events (SOE) should be conducted. In addition, if at any time up to ^{CCI}
[REDACTED]

^{CCI}
[REDACTED] all procedures that were conducted at that visit will be collected in the electronic case report form (eCRF) as an unscheduled visit.

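### SAP 5.6 ends duration of exposure at the last visit of each phase, so the descriptive exposure summary reports time in phase as days on treatment

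*SAP*

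**What the plan says.** SAP 5.6 introduces the three formulas with "Total duration of exposure to study treatment is defined as follows". They are:

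- IBT: "Date of last study visit in IBT – Date of first dosing date + 1"
- Continued blinded treatment (CBT): "Date of last study visit in CBT phase – Date of the CBT Visit 1 dosing of study treatment + 1"
- Open label (OL): "Date of last study visit in OL – Date of the OL Visit 1 dosing of study treatment + 1"

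The end point in IBT is thus "Date of last study visit in IBT", and the other two phases follow the same pattern.

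SAP Table 2 then lists, under treatment compliance, "n, mean, SD, median, min, and max number of days on treatment". Protocol 9.3.7.1 asks for a summary of treatment duration. SAP section 14, which lists departures from the protocol, has no entry on this point, and nothing else in the unredacted text redefines exposure.

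Protocol 3.1.4 says that anyone who has had at least one dose "should be encouraged to complete all study visits within the IBT phase". Those who leave early are asked back for an early termination (ET) visit about 28 days after their last dose; Protocol 3.1.5 sets the same visit after a dose-limiting toxicity (DLT). Protocol 3.1.6 allows visits to go on while drug is interrupted. Protocol 6.4.1 and 6.4.2 place a safety visit about 28 days after the last dose in CBT and OL.

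**The concern.** Duration of exposure should say how long subjects were on drug. A formula that ends at a visit says how long they were followed. The two agree closely only while subjects keep dosing to near the end of the phase. This protocol expects some not to: Protocol 3.1.7 lists many findings that end dosing permanently, and Protocol 3.1.4 keeps dosed subjects in follow-up where possible. For subjects who stop drug and stay, the statistic cannot register the stop.

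The SAP is also uneven with itself. SAP 9.1.5 assigns an adverse event that starts after the last dosing date to the follow-up period, while SAP 5.6 can count that same day as treatment exposure. Safety and tolerability are the primary endpoint, so the exposure table will be read beside the adverse event tables.

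**Working it through.** The plan gives no exposure figure to reproduce, so the check is date arithmetic.

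**Inputs.** First dose on Day 1 (Protocol 3.1.3). Week 12 visit on Day 85 (Protocol 6.4). ET visit 28 days after last dose (Protocol 3.1.4 and 3.1.5). The dosing interval and the day of the last planned dose are redacted. I assume an interval of 14 to 28 days and a last planned dose on Day 57 to Day 71.

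**Formulas**, with last dose on day *d* and interval *I*:

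- SAP rule: last visit day − 1 + 1 = last visit day
- Last-dose rule: *d* − 1 + 1 = *d*
- Last dose plus one interval: *d* − 1 + *I*

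**Subject stops drug but attends Day 85.** The SAP rule gives 85 days whatever *d* is.

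| Last dose | SAP rule | Last-dose rule | Plus 14 days | Plus 28 days |
|---|---|---|---|---|
| Day 1 | 85 | 1 | 14 | 28 |
| Day 29 | 85 | 29 | 42 | 56 |
| Day 57 | 85 | 57 | 70 | 84 |

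For the Day 1 case, the excess over the last-dose rule is 85 − 1 = 84 days. With the interval added, the overstatement is 85/28 = 3.0 to 85/14 = 6.1 times.

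**Subject leaves through the ET visit, counted as the last IBT visit.** The SAP rule gives *d* + 28.

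- Excess over the last-dose rule: (*d* + 28) − *d* = 28 days
- Excess with one interval added: (*d* + 28) − (*d* − 1 + *I*) = 29 − *I*, which is 1 day for *I* = 28 and 15 days for *I* = 14

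**Illustrative arm of 8 PT101 subjects, all attending Day 85.** The SAP mean is 85 days however many stop early. Suppose 2 of 8 have their last dose on Day 29 and the other 6 on Day 57 or Day 71. The last-dose mean is (6 × 57 + 2 × 29)/8 = 50.0 days or (6 × 71 + 2 × 29)/8 = 60.5 days. With no early stoppers it would be 57 or 71 days. Early stopping therefore lowers the last-dose mean by 7.0 to 10.5 days and the SAP mean by nothing.

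**The case against.** The strongest reply is that nothing of consequence rests on this formula, and most of that stands.

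- A reader might infer that exposure is the denominator for the safety results. The documents do not support this. SAP 9.1.6 reports numbers and percentages of subjects, no exposure-adjusted rate is planned, and SAP section 9 rules out inferential testing on safety. The DLT model in SAP 13.1 works on DLTs within a fixed window from dosing, and SAP 5.6 is not among the analyses SAP section 13 lists for the Data Review Committee.
- A reader might infer that tolerability at higher doses will look better than it was. That is not shown. Table 2 and SAP 5.6 also report number of doses, missed doses and cumulative dose. SAP 9.1.6 tabulates adverse events leading to discontinuation, and Table 2 gives discontinuations by reason. The one-dose subject would appear with one dose and a low cumulative dose.
- A reader might infer that everyone who stops for toxicity is credited like a completer. After a DLT, Protocol 3.1.5 specifies an ET visit 28 days after last dose. A DLT after a single Day 1 dose would then give 29 days, not 85. Full credit goes only to those who stop drug and still complete the visits.
- Whether the ET and safety follow-up visits count as the last visit of a phase is not settled by the unredacted text. SAP section 12 names safety follow-up separately from CBT and OL, so the 28-day tail may not arise in those phases.

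What does not stand is the suggestion that the other tables make the duration figure acceptable. They would expose the error, with a full duration shown beside very few doses, but they do not correct it.

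**Conclusion.** The definition is wrong for what it claims to measure: it gives time in phase under a treatment-exposure label. The size depends on how the subject leaves. For a subject who stops drug and completes the IBT visits, the whole phase is credited: 85 days for a single Day 1 dose, against 1 day by last dose or 14 to 28 days with the assumed interval. For a subject who leaves through the ET visit, the excess is 28 days against the last-dose rule, or 1 to 15 days with the assumed interval, on the condition that the ET visit counts as the last IBT visit. The formula and its effect on stoppers who stay are certain. The figures with an interval, and the arm means, rest on assumed values because the schedule is redacted.

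The effect is confined to the descriptive exposure summary. It alters no adverse event percentage, no DLT estimate and no dose count.

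**What to change.** In SAP 5.6, define duration of exposure in each phase from the last dosing date in that phase. Either last dose minus first dose plus 1 will do, or last dose minus first dose plus one pre-stated dosing interval in place of the 1, truncated at death or at the first dose of the next phase. Report time in phase separately, under that name, and state whether ET and safety follow-up visits count towards it. Neither version subtracts interruptions, so keep the missed-dose summary beside it.

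The cost is three formulas and one additional row in Table 2. No new data are needed, since SAP 9.1.5 already uses the last dosing date. The downside is that reported durations become shorter, and the convention for the final interval must be stated for each regimen, because SAP 3.1 describes the Cohort 1 schedule separately from that of Cohorts 2 and 3. This changes an analysis definition only; no dosing or clinical rule is touched.

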## **6 EFFICACY ANALYSES**

Efficacy analyses will be primarily based on the ITT, and the FAS, if different. The efficacy analyses will also be performed on the PP for confirmatory purposes.

### **6.1 DERIVATION OF EFFICACY MEASUREMENTS**

#### **6.1.1 MAYO SCORE**

The Mayo clinic score (MCS) is a composite index of 4 disease activity variables that measures disease severity in UC ([Appendix B](#)). This composite index consists of 2 subject-reported variables (stool frequency [SF] and rectal bleeding [RB]), a physician’s global assessment (PGA) of disease severity and findings on endoscopy. The individual components of the MCS are scored on a 4-point scale (0 to 3 points). These individual variables are summed up to give a total disease activity score that ranges from 0 to 12.

##### **6.1.1.1 Modified Mayo Score**

The mMCS is defined as the total MCS without the PGA subscore and ranges from 0 to 9.

##### **6.1.1.2 Partial Mayo Score**

The pMCS includes 3 components of the total MCS (bowel frequency, RB, and PGA) and excludes the endoscopy subscore. The pMCS score ranges from 0 to 9 with higher scores representing more severe disease activity.

##### **6.1.1.3 Mayo Endoscopic Subscore**

The MES assesses disease activity on a 4-point scale (0 to 3 points), with higher scores representing more severe disease activity.

##### **6.1.1.4 Calculation Rules**

For the purpose of calculation of the MCS/pMCS/mMCS and component subscores, an anchor date is assigned and SF and RB records (from patient diary data) prior to the anchor date are used in the calculation of the subscores.

For screening and post-baseline calculation of MCS, mMCS, SF, and RB, the anchor date is considered the date of the endoscopy. As MES will be only evaluated during the screening visit and not on Day 1 (randomization visit), screening MCS and MES will be used as baseline evaluation.

For all calculations at other visits, including randomization, the anchor date is the date of the study visit. If a CCI CCI endoscopy was not performed, the CCI CCI study visit date will be used. Because the preparation for endoscopy procedure may impact the validity of the diary data, the patient reported daily SF and RB records collected the day of bowel preparation medication (if applicable) and on the day after endoscopy will not be used in the calculation of SF and RB subscores. Derivation of the SF and RB subscores based upon patient records is outlined in [Appendix B](#).

#### 6.1.1.5 Calculation of Screening and Post-baseline Mayo Score

To meet the entry criteria for the enrollment purpose, the calculation of the screening SF and RB subscores for the purpose of calculation of screening MCS is as follows (refer to eCRF completion guidelines):

1. SF subscore will be based on the average number of stools from the closest 3 days within the last 7 days prior to the endoscopic procedure date, excluding the date of bowel preparation (if applicable) compared to the number of stools per day during the patient UC remission.
2. RB subscore will be based on the average score from the closest 3 days within the last 7 days prior to the endoscopic procedure date, excluding the date of bowel preparation (if applicable).
3. PGA subscore used in the baseline MCS is recorded during the Screening visit.
4. MCS will be left as missing if any of four component subscores is missing.

Subjects who have less than 3 permitted days of diary data during screening are not eligible for randomization.

#### 6.1.1.6 Calculation of Baseline Partial Mayo Score and Post-baseline Stool Frequency, Rectal Bleeding, and Partial Mayo Score

The calculation of baseline pMCS and post-baseline SF, RB, and pMCS use the study visit date as the anchor date. For baseline pMCS, the visit date is Day 1 (randomization visit). The calculation rules are described in [Table 3](#) and [Table 4](#) and are as follows:

1. SF and RB subscores will be based on the average score from the closest 3 days within the last 7 days prior to the visit day, excluding the date of bowel preparation (if applicable).
2. PGA subscore used in the calculation of baseline pMCS is the PGA subscore recorded on Day 1 (randomization visit). At subsequent visits, the PGA subscore used in calculation of pMCS is that recorded within the visit window.
3. pMCS will be considered as missing if any of three component subscores is missing.

For Mayo SF subscore, the excess SF is calculated as the difference between the 3-day average SF and the patient reported normal SF during remission. The average SF will be rounded to the nearest integer to match the following scorings:

- 0 Normal number of stools for this subject
- 1 1 to 2 stools more than normal
- 2 3 to 4 stools more than normal
- 3 5 or more stools than normal

